5.5.1.2 Technical Computational Details for Primary Efficacy Analysis

Subjects who meet relapse criteria are considered as an event of relapse. For relapsed subjects in Phase C, time to event is calculated as the earliest date of time-to-relapse, defined as the time meeting relapse criteria - randomized date + 1. Below are the criteria to determine the relapse time for each relapse criteria:

- 1). If subjects meet the relapse criteria per MADRS and CGI-S assessments of criteria I, which are conducted on different dates, the later assessment date will be used as the relapse event date.
- 2). If subjects meet the relapse criteria per criteria IV, C-SSRS or MADRS, the earliest date of the evaluation that the criteria are met will be used as the relapse event date.
- 3). If subjects meet the relapse criteria per hospitalization due to worsening of depression and are reported as an adverse event (AE), the AE start date will be used as the relapse event date.
- 4). If subjects meet the relapse criteria per lack of efficacy or worsening of depression but are not reported as an AE, the first two criteria stated prior will be checked. The earliest date that criteria 1) or 2) is met will be the relapse event date. If none of the above is applicable, then the discontinuation date will be the relapse date.

Subjects who complete the double-blind treatment period of 26 weeks or discontinue treatment without meeting the relapse criteria (including those who are lost to follow-up during treatment period) in Phase C will be considered as censored observations as

mentioned above. For the withdrawn (rather than lack of efficacy) subjects in Phase C, they are considered as censoring at discontinuation, i.e., time to censor = discontinuation date - randomization date + 1. For the completed subjects, they are considered as censoring at the completion, i.e., time to censor = completion date - randomized date + 1. If the time to event/censor is great than 196 days, the subject, no matter discontinued or completed Phase C, will be considered as censoring at Day 196.

The log-rank test will be used to test the equality of the two survival curves.

Additionally, a nominal 95% confidence interval for the hazard ratio (brexpiprazole vs. placebo) will be provided using the Cox Proportional Hazard model with terms for treatment in the model. Ties in the event times will be handled by using the exact option in SAS PROC PHREG.

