3.8.3.3 Documenting Reasons for Treatment Discontinuation

A subject may discontinue IMP for a number of reasons including those listed below:

- Reasons related to AE:
 - Subject decides to discontinue because of annoyance or discomfort due to a non-serious AE which is not otherwise determined to be an undue hazard
 - Continuing IMP places the subject at undue risk as determined by the investigator (eg, a safety concern that is possibly, probably, or likely related to IMP)
 - SAEs
 - Other potentially IMP-related safety concerns or AEs
- Death
- Reasons unrelated to medical condition (provide detail and review AE history with subject)
- Withdrawal of informed consent (complete written withdrawal of consent form)
- Lost to follow-up

Protocol 331-201-00079

- Pregnancy (see [Section 5.5](#))
- Termination of all or part of the trial by the sponsor

In addition, subjects meeting the following criteria must be withdrawn from the trial:

- Occurrence of any AE, intercurrent illness or abnormality in a laboratory assessment which, in the opinion of the investigator, warrants the subject's permanent withdrawal from the trial
- Treatment with a prohibited concomitant medication other than the use of appropriate medications for the treatment of AEs under direction of the investigator;
- Subject noncompliance, defined as refusal or inability to adhere to the trial schedule or procedures ([Section 3.12](#))
- At the request of the subject, investigator, OPDC or designee, or regulatory authority;
- Subject becomes pregnant
- Subject cannot tolerate the minimum dose of brexpiprazole (ie, 2 mg/day or matching placebo)
- Subject does not fulfill the response criteria by Week 8 of Phase A.
- Subject does not fulfill stability criteria by Week 12 of Phase B. In addition, subjects who have more than 3 excursions (ie, do not meet stability criteria at a scheduled visit) during Phase B and subjects with 3 consecutive excursions or an excursion on the last visit of the Phase B are to be withdrawn. A missed visit during Phase B will be considered an excursion.
- Subjects that do not maintain a stable dose of IMP or ADT for the last 4 weeks of Phase B
- Subject meets criteria for relapse in Phase C
- Subject is lost to follow-up

If the subject discontinues IMP due to an AE, the investigator, or other trial personnel, will make every effort to follow the event until it has resolved or stabilized. Follow up procedures in [Section 3.8.3.2](#) must be followed.

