5.2 Eliciting and Reporting Adverse Events

The investigator will periodically assess subjects for the occurrence of AEs. To avoid bias in eliciting AEs, subjects should be asked the non-leading question: “How have you felt since your last visit?” All AEs (serious and nonserious) reported by the subject must be recorded on the source documents and on the eSource provided by the sponsor. Serious AE collection is to begin after a subject has signed the ICF.

Use medical terminology in AE reporting. Adverse events should be reported as a single unifying diagnosis whenever possible or, in the absence of a unifying diagnosis, as individual signs or symptoms. Exacerbation or disease progression should be reported as an AE only if there are unusual or severe clinical features that were not present, or experienced earlier, or not expected based on the course of the condition.

A reported AE that undergoes a change in severity, seriousness, or toxicity should be reported as a new AE on the source documents and on the eSource provided by the sponsor.

In addition, the sponsor must be notified immediately by telephone, fax, or e-mail of any IREs according to the procedure outlined below, in [Section 5.3](#). Special attention should be paid to recording hospitalization and concomitant medications.

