7.4.4 Interim Analysis

Two interim analyses are planned for assessment of efficacy. These analyses are planned to be performed following a group sequential approach at approximately 50% and 75% of events accrual time points and will include all randomized subjects. The second interim analysis (at 75% of events) will be performed only if the first interim analysis is not positive. Subjects who withdraw early from the trial or who are still in the trial at the end of Week 46 will be considered as providing censored observations. The O'Brian-Fleming boundaries will be used for the interim analysis so that the first interim analysis will be conducted when 52 relapse events are available and the second interim analysis, if needed, will be conducted when 78 relapse events are available (Table 7.4.4-1).²⁸ The 2-sided alpha levels for these two interim analyses are 0.003051 and 0.018325 respectively, and the alpha left for the final analysis will be 0.044005. Additionally, a 95% confidence interval for the hazard ratio (brexpiprazole + ADT vs placebo + ADT) will be provided

Protocol 331-201-00079

using the Cox Proportional Hazard model with term of treatment in the model. If the null hypothesis is rejected at either interim analysis time point, the trial will be terminated for having achieved the primary endpoint of a significantly lower incidence with brexpiprazole + ADT compared with placebo + ADT. A separate Relapse Event Evaluation Committee will review and track each relapse event identified and documented. An Interim Analysis Plan will be developed to document the details of data flow and other logistical considerations relating to the interim analyses.

Table 7.4.4-1 Boundaries for Rejection of Null Hypothesis for Interim and Final Analyses		
Analysis	Number of events	2-sided alpha Level^a
Interim analysis #1 (~50%)	52	0.003051
Interim analysis #2 (~75%)	78	0.018325
Final analysis (100%)	104	0.044005

^aObtained using PASS 14 sample size software.

The interim monitoring of efficacy will be performed by an independent IARC (Section 3.7.7). Should the interim analysis be performed at a different time, different frequency, the spending function approach as originally introduced by Lan and DeMets²⁹ will be applied to adjust the critical values in order to guarantee an overall 0.05 alpha level. The spending functions corresponding to O'Brien-Fleming boundaries will be formally applied to the time-to-event analysis (using the log-rank test).

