5.5 Efficacy Analysis

5.5.1 Primary Efficacy Analysis

5.5.1.1 Primary Efficacy Endpoint

The primary efficacy endpoint of this trial is time-to-relapse by any criteria as defined in the blinded addendum to this protocol, measured from Week 20 (randomization) to the Double-blind, Randomized Withdrawal Treatment Phase).

Time-to-relapse (primary efficacy endpoint) is defined as meeting any of the following criteria (blinded to investigators) measured from randomization into Phase C:

- I. At the same visit, an increase on the MADRS total score of 50% from randomization and CGI-S score ≥ 4 , **OR**

- II. Hospitalization for depression, **OR**
- III. Discontinuation for lack of efficacy or worsening of depression, **OR**
- IV. Active suicidality, defined as a score of ≥ 4 on the MADRS item 10 **OR** an answer of “yes” on question 4 or 5 on the C-SSRS **OR** an answer of yes to any of the questions on the Suicidal Behavior section of the C-SSRS.

The time origin for measuring this event time is the date of randomization into the double-blind, placebo-controlled treatment phase (Phase C). Phase C Efficacy Sample is used in the primary analysis of the primary efficacy endpoint. The primary objective of statistical analysis is to compare the efficacy of brexpiprazole (2 to 3 mg/day) + ADT with that of placebo + ADT with regard to time-to-relapse. This will be achieved by testing the equality of the two survival curves by the log-rank test.

Interim analyses are planned to be performed at approximately 50% and 75% of events accrual time points using the O’Brian-Fleming boundaries for rejection of the null hypothesis. Details of the interim analyses are provided in the interim analysis plan.

A group sequential testing procedure will be employed with two planned interim analyses at approximately 50% (52 events) and 75% (78 events) events accrual time points, and a final analysis using 100% (approx. 104 events) events. The O’Brian-Fleming boundaries will be utilized in this analysis for the rejection of the null hypothesis to maintain an overall nominal significance level of 0.05 (two-sided). [REDACTED]

[REDACTED]

[REDACTED]

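### SAP 5.5.1.2 can censor a criterion III relapse: discontinuation for worsening of depression recorded as an adverse event without hospitalization has no specific event date, and the censoring sentence does not exempt it

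*SAP*

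**What the plan says.** SAP 5.5.1.1 lists four routes to relapse. The third is "Discontinuation for lack of efficacy or worsening of depression". It makes no exception for worsening that is recorded as an AE.

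SAP 5.5.1.2 opens with a general rule: "Subjects who meet relapse criteria are considered as an event of relapse". Its general censoring rule applies to subjects who complete or who "discontinue treatment without meeting the relapse criteria". SAP 5.5.1.1 agrees, censoring early withdrawals only when there was no relapse event.

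Four dating rules follow the opening of 5.5.1.2:
- Rule 1 dates criterion I (MADRS with CGI-S).
- Rule 2 dates criterion IV (suicidality).
- Rule 3 dates hospitalization for worsening that is reported as an AE, using the AE start date.
- Rule 4 begins "If subjects meet the relapse criteria per lack of efficacy or worsening of depression but are not reported as an AE". It takes the earliest date under rule 1 or 2, and otherwise the discontinuation date.

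The section then adds: "For the withdrawn (rather than lack of efficacy) subjects in Phase C, they are considered as censoring at discontinuation".

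On recording, Protocol 5.2 says: "Exacerbation or disease progression should be reported as an AE only if there are unusual or severe clinical features". On event review, Protocol 7.4.4 says: "A separate Relapse Event Evaluation Committee will review and track each relapse event identified and documented".

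**The concern.** The censoring sentence names one limb of criterion III and omits the other. Rules 3 and 4 divide worsening by whether it was reported as an AE, but the AE side is covered only when the subject was hospitalized. One combination therefore has no dating rule of its own and, read literally, falls under the censoring sentence.

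The combination can occur. Protocol 5.2 allows worsening to be an AE when it has unusual or severe features. Investigators do not know the relapse criteria (SAP 3.2 and 5.5.1.1), so a site cannot be expected to change an AE withdrawal to lack of efficacy in order to satisfy a criterion it cannot see. Protocol 3.7.1.4 also says that no efficacy scales are done at early termination if a new antidepressant has already been started. In that case criterion I cannot be shown at that visit.

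At stake is the status of some primary events. Two programmers could both follow SAP 5.5.1.2 and classify the same subject differently. The result affects the hazard ratio and the event count that triggers two looks, either of which can end the trial.

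**Working it through.** **Step 1. Routes for a Phase C subject who stops because depression worsened.**

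| How it is recorded | Criterion met | Specific dating rule |
|---|---|---|
| Not an AE | III | Rule 4 |
| AE, hospitalized | II | Rule 3 |
| AE, not hospitalized, also meets I or IV | I or IV | Rule 1 or 2 |
| AE, not hospitalized, meets neither I nor IV | III | None |

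Only the last row is open. Criterion III and the two general rules make this subject an event. The censoring sentence, read literally, censors the subject at discontinuation.

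**Step 2. Reproduce the plan's figure** (Protocol 7.1, SAP 4: relapse risks 30% and 16%, 104 events, 95% power, 2-sided 0.05; Protocol 7.4.4: levels 0.003051, 0.018325 and 0.044005).
- Hazard ratio = ln(1 − 0.16) / ln(1 − 0.30) = 0.489, stated as 0.49.
- Schoenfeld events = 4(1.960 + 1.645)² / (ln HR)², which gives 102 at 0.489 and 103 at 0.49. Freedman's formula gives 111 and does not match.
- Simulation of the three looks at the stated levels (2,000,000 draws) gives overall alpha 0.0498 and power 95.1% at 104 events with HR 0.49.

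The plan's 104 events and 95% power are confirmed, and the concern does not dispute them.

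**Step 3. Shift in the hazard ratio.** The documents give no count of affected subjects, so the losses here and below are assumptions. With 225 per arm and no dropout, expected relapses are 225 × 0.30 = 67.5 on placebo and 225 × 0.16 = 36 on brexpiprazole. If five events are not counted:
- All on placebo: ln(1 − 36/225) / ln(1 − 62.5/225) = 0.54.
- All on brexpiprazole: ln(1 − 31/225) / ln(1 − 67.5/225) = 0.42.
- In proportion (3.3 and 1.7): 0.49, unchanged.

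**Step 4. Timing of the looks.** Suppose m of every 104 true relapses go uncounted, at a constant rate. A look set at D counted events then happens after D × 104/(104 − m) true relapses.
- m = 5: 52 becomes 54.6, 78 becomes 81.9 and 104 becomes 109.3.
- m = 15: 52 becomes 60.8, 78 becomes 91.1 and 104 becomes 121.5.

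**Step 5. Power, only if lost events are never replaced** (HR 0.49, same three-look simulation).

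| Events lost | Events left | Power |
|---|---|---|
| 0 | 104 | 95.1% |
| 5 | 99 | 94.1% |
| 10 | 94 | 92.9% |
| 15 | 89 | 91.6% |
| 20 | 84 | 90.0% |

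SAP 4 lets enrolment vary in order to reach 104 events, so Step 4 is the more likely consequence.

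**The case against.** The strongest defence is that the disputed sentence is shorthand. It follows the general censoring rule and supplies the time formula. SAP 3.4 says relapsing subjects are withdrawn for lack of efficacy, so that label may be meant to cover all of them. Read alone, the sentence would also contradict rule 4 for worsening not reported as an AE, which suggests it was never meant literally. A reader might infer that the SAP censors every withdrawal not labelled lack of efficacy. The documents do not support this: both general rules make anyone who meets a relapse criterion an event, and rule 4 counts non-AE worsening. The shorthand reading still leaves a gap, because sites are blinded to the criteria and their recorded reason need not follow the label.

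There is also a general date definition in 5.5.1.2, the time at which the criteria are met, so an event date can be argued for. It does not settle whether that is the AE start date (as in rule 3), an earlier assessment date or the discontinuation date (as in rule 4).

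The group is probably narrow. Severe worsening will often meet criterion I, II or IV, and the early termination visit normally includes MADRS, CGI-S and C-SSRS. This stands, and it limits the size of the problem.

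A reader might infer from the reason list in Protocol 3.8.3.3, which has no entry for lack of efficacy or worsening, that misrouting is likely. The list is introduced as non-exhaustive, the same section requires withdrawal on relapse, and the eSource categories are not shown. Nor do the documents establish that the Relapse Event Evaluation Committee would miss these cases. They describe its work on identified events and do not say how events are identified.

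The sensitivity analyses in SAP 5.5.2 address informative censoring. One simulates event times for censored dropouts at the placebo hazard, multiplied by k of at least 1 on brexpiprazole. The other counts a random 20% of brexpiprazole discontinuations as events. They are useful stress tests, but neither restores an actual relapse at its actual date.

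**Conclusion.** The concern holds as a conflict within the primary endpoint rules. SAP 5.5.1.2 gives no specific date for discontinuation due to AE-reported worsening without hospitalization, and its censoring sentence exempts only lack of efficacy. Subjects in this group who do not also meet criterion I or IV could be censored contrary to criterion III and to the general rules in 5.5.1.1 and 5.5.1.2.

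The number affected and the split by arm are unknown. The main effects would be misclassified primary events, a possible shift in the hazard ratio in either direction (0.42 to 0.54 for five events, at the extremes of allocation), and later looks. A definite loss of power is a tempting reading, but it does not follow in a trial that runs to 104 events. Even 15 unreplaced losses would leave 91.6%. If losses fell mainly on placebo, the bias would be against brexpiprazole. The case for fixing this rests on an ambiguous primary event, not on a demonstrated large effect.

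**What to change.** Make two changes to SAP 5.5.1.2 before unblinding, and apply the same rule at both interim looks and the final analysis:

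1. In the censoring sentence, replace the parenthesis with *without meeting any of relapse criteria I–IV*.
2. Extend rule 4 to discontinuation for worsening of depression whether or not it is reported as an AE: the earliest date under rule 1 or 2, otherwise the discontinuation date. Leave rule 3 for hospitalizations.

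The cost is two sentences and the matching program change. No new data are needed.

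Two safeguards are optional. The existing Relapse Event Evaluation Committee could review Phase C discontinuations blinded, which adds a small judgement step. A discontinuation reason for lack of efficacy or worsening of depression could be added in eSource. Neither is needed to resolve the conflict.

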5.5.2 Sensitivity Analysis for the Primary Endpoint

In order to assess the effect of potential informative censoring prior to the scheduled 26 weeks of treatment in Phase C, two approaches of sensitivity analysis will be adopted to estimates this effect on the primary efficacy analysis results. These are: (1) multiple imputation of discontinued censored observations using the estimated hazard rate from the placebo group, (2) treating 20% of randomly selected discontinued patients only from the brexpiprazole group as events. These methods of sensitivity analyses are described below. Subjects who discontinued in Phase C because of trial termination by the sponsor will not be imputed in the final analysis.

5.5.2.1 Multiple Imputation Method

Assume that the time to event variable follows an exponential distribution. The following multiple imputation method will be used to impute time to event from their time of discontinuation for censored subjects in the sensitivity analysis.

For a placebo + ADT subject, assume the hazard of the subject to develop an event is identical to the estimated hazard of the placebo + ADT group (hazard estimated at interim analysis for sensitivity analysis of the interim analysis and hazard estimated in the final analysis for sensitivity analysis of the final analysis). Event time will be simulated for the subject using an exponential distribution with the rate parameter (λ) equal to the estimated hazard of the placebo group. This same rate is used to simulate Event time of all dropout subjects from both brexpiprazole and placebo treatment groups; except that the placebo group will use the rate without modification and the brexpiprazole group will use the rate multiply by a factor equal to or greater than 1. The time to event of the subject is equal to the sum of the time to discontinuation and the simulated event time of the subject. If the time to event of the subject is greater than 196 days from

randomization, then the subject will be censoring at 196 days from randomization with no event. Otherwise, the subject will have an event at the time to event as calculated above.

For a brexpiprazole + ADT treated subject, the imputation of time to event or time to censor (if the simulated event is greater than 196 days) is similar to the imputation of placebo treated subject, except that the exponential distribution will have a rate parameter equal to $k * \lambda$, where λ is the hazard rate of the placebo group and $k \geq 1$.

For each imputation, the simulated data will be combined with the data for subjects who complete the double-blind treatment period of 6 months without an event and subjects with events, to obtain the log-rank test and in the time to event analysis using Cox Proportional Hazard model with treatment as the independent variable. For each k , 30 imputations will be performed. The results of these thirty imputations will be combined using SAS PROC MIANALYZE to provide a final result for this k . The k will run from 1.0 to 1.1, 1.2, ..., until the test loses its significance.

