3.7 Interim Analysis Review Committee

The Interim Analysis Review committee (IARC) is formed to independently review unblinded efficacy data for the planned interim analyses (at approximately 50% and 75% of protocol event accrual) and make recommendations to the sponsor. Details are described in the IARC Charter for the Protocol.

[figure not shown]

Figure 3-1

Trial Design Schematic

4 Sample Size and Power Justification

The primary objective of this trial is to show superiority of brexpiprazole (2 to 3 mg/day) + ADT over placebo + ADT in time to relapse of MDD signs and/or symptoms. The 2-sided log-rank test will be used to test for statistical significance of the differences between the 2 survival curves.

Based on the results from a completed randomized withdrawal trial of olanzapine/fluoxetine combination versus fluoxetine monotherapy to assess prevention of relapse in subjects with treatment-resistant depression, it is reasonable to expect that 30% of subjects who receive placebo and 16% of subjects treated with brexpiprazole will relapse in 6 months, a hazard ratio of 0.49 (brexpiprazole + ADT versus placebo + ADT) is derived. Thus, 104 relapse events are needed in this trial to reach 95% power to test the primary hypothesis of the protocol at a 2-sided 0.05 alpha level. The sample size estimates used a 1:1 randomization ratio (brexpiprazole + ADT: placebo + ADT) which allowed 2 interim looks at 50% and 75% of events accrual time points. The O'Brian-Fleming boundaries were used for sample size calculation of the interim analysis so that the first interim analysis will be conducted when 52 relapse events are available, and the second interim analysis will be conducted when 78 relapse events are available. The 2-sided alpha levels for these 2 interim analyses are 0.003 and 0.018 respectively, and the alpha left for the final analysis when 104 relapse events are available will be 0.044.

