While the interim analysis follows the boundaries listed in Table 5.5.1.1-1, “final” analysis must be performed after a recommendation based on the interim analysis. This “final” analysis will include the relapse events that occur between the data cutoff for the interim analysis and the final database lock, and the alpha level for the “final” analysis will be derived based on the total number of events using O’Brian-Fleming spending function. Should the interim analysis be performed at a different time, different frequency, the spending function approach as originally introduced by Lan and DeMets will be applied to adjust the critical values to guarantee an overall 0.05 alpha level. The

spending functions corresponding to O'Brien-Fleming boundaries will be formally applied to the time-to-event analysis (using the log-rank test).

For the primary endpoint, a 95% confidence interval for the hazard ratio (brexpiprazole (2 to 3 mg/day) + ADT with that of placebo + ADT) will be provided using the Cox Proportional Hazard model with treatment as the fixed effect in the model.

The Phase C Efficacy Sample will be used in the above analysis. Subjects who withdraw early from the trial without relapse events or who are still in the trial at the end of the Week 46 will be considered as censored observations at the discontinuation or completion date. If the time to event of the subject or completion date is greater than 196 days from randomization, then the subject will be censored at 196 days from randomization with no event. Subjects who stay in the trial but have no relapses in an interim analysis will be censored at the date of data cut-off for the interim analysis.

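### The multiple-imputation sensitivity analysis does not place subjects still in Phase C, or stopped by the sponsor, in its data sets, and it counts imputed relapses 11 to 15 days after completers leave the risk set

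*SAP*

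**What the plan says.** SAP Section 5.5.2 names two sensitivity analyses for informative censoring. The first, in Section 5.5.2.1, draws an exponential relapse time for each dropout. The rate is the placebo hazard for placebo dropouts and k times that hazard for brexpiprazole dropouts. Each of 30 imputations is analysed by log-rank test and Cox model, and k rises from 1.0 in steps of 0.1 until significance is lost.

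On the make-up of each data set, Section 5.5.2.1 says "the simulated data will be combined with the data for subjects who complete the double-blind treatment period of 6 months without an event" and with subjects who had events. Section 5.5.2 adds: "Subjects who discontinued in Phase C because of trial termination by the sponsor will not be imputed in the final analysis". For the primary analysis, Section 5.5.1.1 covers ongoing subjects: "Subjects who stay in the trial but have no relapses in an interim analysis will be censored" at the data cut-off.

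On the time horizon, the rule in Section 5.5.2.1 begins "If the time to event of the subject is greater than 196 days from" randomization; such a subject is censored at Day 196, and any earlier imputed time counts as a relapse. Section 5.5.1.2 censors completers at their own completion date, counted from randomization plus one day.

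**The concern.** There are two separate problems.

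**Membership.** A subject still in Phase C at an interim cut-off has no discontinuation to impute from, has not completed and has no event. A subject stopped by the sponsor is in the same position. Neither belongs to any of the three listed groups. A programmer who follows the list would discard their event-free time and keep relapses from the same recently randomized cohort, which is selection on outcome. The situation is foreseen by the plan: Section 5.5.2.1 provides for a hazard estimated at the interim, and Protocol Section 7.4.4 terminates the trial if the null hypothesis is rejected at either interim.

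**Horizon.** In the primary analysis Day 196 is only an upper limit on observed time. In the imputation it creates events after planned follow-up has ended. Once completers have left, nearly everyone at risk is an imputed dropout, and among them the hazard ratio equals k by construction.

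At stake is how the tipping-point k is read. It should measure sensitivity to dropout, and both features move it for other reasons.

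**Working it through.** **1. The plan's own figure.** SAP Section 4 assumes that "30% of subjects who receive placebo and 16% of subjects treated with brexpiprazole will relapse in 6 months", giving "a hazard ratio of 0.49". Check: ln(0.84)/ln(0.70) = 0.489. It states that "104 relapse events are needed in this trial to reach 95% power to test the primary hypothesis of the protocol at a 2-sided 0.05 alpha". Schoenfeld's formula at a hazard ratio of 0.49 gives 103 events for a fixed design. With the looks in Protocol Section 7.4.4 ("The 2-sided alpha levels for these two interim analyses are 0.003051 and 0.018325 respectively, and the alpha left for the final analysis will be 0.044005"), simulation gives 95.0% power at 104 events and an overall two-sided alpha of 0.0499. The planning inputs therefore reproduce.

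**2. When completers leave.** Week 46 is 26 weeks after randomization: 26 × 7 = 182 days, or Day 183 on the plus-one count. The visit window of ±2 days (Protocol Table 3.7-3) gives Day 181 to 185. The gap to Day 196 is 196 − 185 = 11 to 196 − 181 = 15 days.

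**3. Relapses that the gap adds.** Placebo hazard: −ln(0.70)/182 = 0.00196 per day. A dropout still event-free at Day 183 has probability 1 − exp(−13 × 0.00196) = 2.5% of an imputed relapse by Day 196. Take N = 450, 20% exponential dropout over 26 weeks and k = 1. Integrating the chance of an imputed relapse over dropout times gives 15.4 expected imputed relapses with the Day 196 limit and 14.0 with Day 185, a difference of 1.4, or 10%.

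**4. Subjects outside the three groups.** Simulation inputs: the relapse rates above, 20% dropout, N = 450 (SAP Section 4), and uniform randomization over the 22 months of recruitment (Protocol Section 3.7). Averages over trials that crossed the boundary:

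| Look | Events | Dropouts | Completers | Ongoing | Share ongoing |
|---|---|---|---|---|---|
| 52 events | 52.0 | 44.5 | 118.6 | 96.1 | 96.1/311.2 = 31% |
| 78 events | 78.0 | 67.9 | 188.3 | 87.7 | 87.7/421.9 = 21% |

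**5. Effect on the result.** The first simulation used 60 significant trials per scenario, 30 imputations, Rubin's rules, the SAP's 0.1 grid and the stated alpha of each look. The corrected version keeps everyone and stops imputed times at Day 183.

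| Scenario | HR at k = 1, literal → corrected | Median tipping k, literal → corrected |
|---|---|---|
| 52 events | 0.409 → 0.391 | 1.00 → 1.15 |
| 78 events | 0.513 → 0.499 | 1.55 → 1.80 |
| 104 events with a stop (N = 560 assumed) | 0.560 → 0.547 | 2.50 → 2.80 |
| Full follow-up, N = 450 (horizon only) | 0.528 → 0.522 | 2.40 → 2.70 |

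A second simulation used 80 boundary-crossing trials per look, a threshold of 1.96 throughout and Day 185 in the corrected version. It gave:

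| Scenario | HR at k = 1, literal → corrected | Median tipping k, literal → corrected |
|---|---|---|
| 52 events | 0.424 → 0.411 | 2.8 → 3.4 |
| 78 events | 0.504 → 0.494 | 2.8 → 3.1 |
| Full follow-up | 0.532 → 0.528 | 2.6 → 3.0 |

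**6. Direction.** In the first simulation the later horizon alone lowered k in 50% to 92% of trials and almost never raised it. The omission alone lowered k in 38% to 53% and raised it in 15% to 20%.

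**The case against.** The strongest reply is that the list is shorthand. Section 5.5.2 frames the method as imputing discontinued, censored observations to test the primary analysis, and that analysis uses the whole Phase C Efficacy Sample. On this view, not being imputed means keeping the observed censoring time. Section 5.5.2.2 also omits ongoing subjects from its list, and nobody would infer that they are deleted there. Interim details are deferred to a separate interim analysis plan, which is not among the documents. This reply has force. A reader might infer that the SAP orders these subjects to be excluded, and the documents do not support that. What stands is that the only statement of the data set's contents leaves them out. Where the SAP wants sponsor-stopped subjects censored it says so, as it does for time to discontinuation in Section 5.5.4.3.2.

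On the horizon, Day 196 is the general Phase C limit, used also for the primary endpoint, functional relapse and time to discontinuation. The tables of week definitions are missing from the text available, so Day 196 may be the limit of the Week 26 window. Some completers will also attend late, so the final stretch is almost, not strictly, dropouts only. None of this removes the mismatch: an upper limit on observed time does not lengthen a completer's follow-up, whereas the same limit lengthens a dropout's imputed follow-up.

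The effect is also modest. A further simulation of 120 boundary-crossing trials per look, comparing the literal rule with the full sample and Day 185, moved the mean z at k = 1 by 0.13, 0.09 and 0.06 (52 events, 78 events, full follow-up). Conclusions at 1.96 hardly changed. That is accepted.

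**Conclusion.** The point holds as a gap in the specification with a modest effect. The listed contents leave out ongoing and sponsor-stopped subjects, possibly through loose wording. The horizon mismatch follows from stated rules and applies even with full follow-up and no early stop.

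Together they move the hazard ratio at k = 1 by about 0.005 to 0.02, towards 1. They lower the median tipping k by 0.15 to 0.3 when the alpha of each look is used, and by up to about 0.6 when 1.96 is used at the interims. Section 5.5.2.1 does not name the level at which significance is lost.

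A reader might infer that the analysis makes a fragile result look sound. The calculations do not support that: the shift mostly lowers k and so understates robustness, although the omission alone can go either way. Nor should this be called the main sensitivity analysis, since the SAP lists two without ranking them. The primary test is unaffected.

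The sizes rest on assumptions outside the documents: uniform accrual, exponential dropout, a placebo rate estimated as events over person-time, and N = 560 in the 104-event scenario. With 60 to 80 trials per scenario the median k values are approximate.

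**What to change.** Change two sentences in SAP Section 5.5.2.1.

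1. Replace the sentence on combining data: each imputed data set contains the whole Phase C Efficacy Sample. Only discontinuations other than sponsor termination are imputed. All other subjects keep their observed event or censoring time, including those ongoing at a cut-off or stopped by the sponsor.
2. Replace the Day 196 limit on imputed times: censor them at the end of the Week 46 visit window (Day 185), so that they share the completers' horizon. Observed events stay as in the primary analysis, under its Day 196 rule.

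This needs no new data and changes neither the primary analysis nor the alpha plan. It should be settled before unblinding, so that the contents of the data set are not left to the programmer. If the interim analysis plan already states the first rule, the SAP can repeat it.
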